whole body-EMS machine. Individuals will be trained in a ratio of 2 subjects to 2 machines and one trainer. Subjects in the control group will undergo training with a similar physical exercise program as those in the interventional group undertaking routine exercise maneuvers (including squatting, lunging, forward flexion etc.), and will use the same equipment and will be ‘dressed’ as if they were undergoing whole body-EMS, but will have no/subthreshold electricity signals applied to their body vest. The EMS machine will be switched on and show normal wave patterns suggesting that it is working normally, but study participants will be blinded to whether or not they are receiving percutaneous electrical stimulation while doing the routine exercise maneuvers. This will be applied for a 16-week training program 1.0 time a week for a maximum of 20 minutes per session, with no intermittent breaks. Individuals will be trained in a ratio of 2 subjects to 2 machines and one trainer. Individuals will be randomized to each group, and they and the study investigators will be blinded to the intervention. Otherwise, individuals in both groups will be asked to maintain their normal lifestyles.

In order to generate a safe, individualized, joint-friendly, and time-efficient exercise protocol which will be potentially effective and feasible for a cohort that may have physical limitations, we plan to implement the same previously utilized whole body-EMS training protocol successfully applied in other whole body-EMS trials undertaken in Germany that have focused on body composition and functional parameters (1-4). Briefly, with the whole body-EMS equipment (miha bodytec®, Gersthofen, Germany) we will apply a simultaneous but region specific stimulation of all the main muscle groups with an overall area of up to 2750 cm². We will consistently run an guided whole body-EMS program in groups who will always supervised

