and guided by two certified instructor (i.e., two applicants coached by one instructor). Whole body-EMS will be conducted on approximately the same day, once a week (i.e., $1.0 \times \text{week}$) for 20 minutes. The device will apply a bipolar electric current; we will select an impulse frequency of 85 Hz, an impulse width of 350 μs , and will apply an interval approach with 4 seconds of stimulation alternating with 4 seconds of rest. Gentle slight dynamic exercises will be performed during the 4-second stimulation phase. Each session will consist of 10–14 dynamic exercises structured in one to two sets of eight repetitions performed without any additional weights in a standing position. Most exercises will be based on a low amplitude squat exercise ($< 35^\circ$ leg flexion) with full amplitude movements of the arms (such as rowing, lat pulley, or butterfly). The emphasis of the protocol however will not be the effect on muscles induced by voluntary activation but by the application of whole body-EMS with high current intensity during functional movements. During the course of the study, the instructor will progressively increase the volume of stimulation by extending the length of the session from 14 up to 20 minutes after 4 weeks of training. The intensity of the stimulation will be regulated using a rate of perceived exertion (RPE) scale to generate a sufficient, but tolerable, intensity of EMS application to all stimulated areas. For each of the muscle groups stimulated, participants will be encouraged to exercise at a RPE of “6–7 out of 10” (i.e., “hard+ to very hard”) on the Borg CR10 Scale (5). This specification will be achieved in close interaction between the participant and instructor. Based on initial start settings determined after 4, 8, and 12 weeks, the impulse intensity will be increased slightly every 3 minutes to maintain/slightly increase the prescribed RPE during each session (**refer to Supplemental Video**).

Schedule of events

| | Baseline Day 0 | Weeks 1-7 | Week 8 follow-up (+/- 7 days) | Weeks 9-15 | Week 16 follow-up (+/-7 days) |
|---|----------------|-----------|-------------------------------|------------|-------------------------------|
| Informed Consent | X | | | | |
| Brief review of medical history | X | | | | |
| Exercise with EMS device | X | X | X | X | X |
| Blood draw and laboratory testing** | X | | | | X |
| Creatinine Kinase | X | | X | | X |
| Physical Assessment* | X | | | | X |

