Peripheral Endothelial Function: Endothelial function will be measured via the RH-PAT index as previously described (6-9). The studies will be performed in a designated quiet, temperature controlled and uniformly lit room. Individuals in the interventional and control groups will be tested at baseline, and will undergo re-testing after completing 16-weeks of training within their assigned arm (within 2 weeks of completion). Subjects will be fasting for 4 hours before the study and will abstain from coffee or tobacco use on the day of the examination. Subjects taking any vasoactive medications, including calcium channel blockers, nitrates, ACE-inhibitors or beta blockers, will discontinue these for 24 hours prior to testing. The study will be conducted in the sitting position in a comfortable chair with armrests. A fitted blood pressure cuff will be placed on one arm, and the finger cuffs of the Endo-PAT 2000 device (Itamar Medical Inc. Ltd., Caesarea, Israel) will be placed on one finger of each hand (10). Subjects will relax for 10 minutes before initiation of the protocol. Baseline blood pressure and heart rate will be obtained via a digital automated blood pressure cuff (Omrom Healthcare, Inc., Vernon Hills, Illinois). The EndoPAT 2000 will be used specifically in this study because it is a Food and Drug Administration–approved noninvasive device, it allows continuous recording of the signal, and interpretation of the data is operator independent. The use of a control arm will allow the elimination of systemic interference of the test and independence from the participant’s knowledge or conscious control of the signals (10-14). The finger probes consist of inflatable latex air cuffs connected by pneumatic tubes to an inflating device controlled through a computer algorithm. A constant counter pressure

(predetermined by baseline diastolic blood pressure) will be applied through the air cushions. This prevents venous pooling and thereby venoarteriolar reflex vasoconstriction while not occluding arterial blood flow. Pulsatile volume changes of the distal digit induce pressure alterations in the finger cuff, which are sensed by pressure transducers and transmitted to and recorded by the Endo-PAT device. A decrease in the arterial blood volume in the distal fingertip causes a decrease in pulsatile arterial column changes, reflected as a decrease in the measured PAT signal, and vice versa.

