Questionnaires: Baseline clinical characteristics of all the participants will be carefully determined with validated baseline questionnaires (16). Completeness and accuracy of the questionnaires will be carefully checked by research assistants in close cooperation with the participants. In addition, all participants will complete four additional questionnaires at baseline, and 16-weeks follow-up in each of the intervention and non-intervention arms as follows:

- i) Rose Questionnaire Is a validated questionnaire that has been used previously to assess for symptoms of angina (17)
- ii) Linear Analog Self-Assessment (LASA) Mayo Clinic has developed a series of items that asks adults to rate their level of functioning on a scale from 0 (as bad as it can be) to 10 (as good as it can be). The six items to be used in this study inquire about overall quality of life, and then cover the five domains of quality of life: (1) mental well-being, (2) physical well-being, (3) emotional well-being, (4) social well-being, and (5) spiritual well-being.(18, 19)
- iii) Patient Health Questionnaire-9 (PHQ-9) This is a questionnaire commonly used in clinical practice to assist in the assessment of patients who are suspected to have features consistent with a diagnosis of depression
- iv) Perceived Stress Scale (PSS) This is a 14-item self-report tool that provides a global measure of perceived stress.(20) Responses range on a 5-point scale from “never” to “very often.” A higher score indicates greater stress. The PSS correlates well with

life-events stress measures and social anxiety, and has adequate reliability ($\alpha = .84, .85, .86$) in three different samples.

i)

ii) **Standing Balance:** For standing balance test, participants will first stand on a portable force plate (Model6090-06, Bertec, Columbus, OH) with two feet as steady as possible for 30 seconds with eyes open. Then, the same procedures will be repeated with eyes closed. Next, the low back region will be strapped with a vibration device to stimulate the muscle spindles of the low back muscles during eyes-open and –closed balance. A total of three trials will be collected. Position and velocity data about the center of pressure (CoP) of the body will be calculated and used for analysis.

Statistical Analysis

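### Participant blinding is unlikely to hold as sessions are written: active current is titrated to felt effort, while controls get an undefined or absent current and no matching adjustment routine

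*Combined protocol and SAP*

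**What the plan says.** Trial Design calls the study blinded. Intervention adds that "study participants will be blinded to whether or not they are receiving percutaneous electrical stimulation", and that the study investigators are blinded too. It does not say whether the instructor, who operates the device, is blinded.

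The masking for controls is a similar exercise programme, the same equipment and dress, and a device that runs and displays ordinary waveforms. On the current, the text says only that they are dressed as for EMS "but will have no/subthreshold electricity signals applied to their body vest". It does not choose between the two options or say whether the threshold is sensory or motor.

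The active dose is set by sensation. "For each of the muscle groups stimulated, participants will be encouraged to exercise at a RPE of" 6–7 out of 10 on the Borg CR10 scale. "This specification will be achieved in close interaction between the participant and instructor". Then "the impulse intensity will be increased slightly every 3 minutes to maintain/slightly increase the prescribed RPE during each session". The same paragraph says the emphasis is on the high-intensity current rather than on voluntary effort.

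On set-up: "Individuals will be trained in a ratio of 2 subjects to 2 machines and one trainer". The plan gives this ratio once for each arm and does not say whether a pair must come from the same arm.

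On outcomes, "all participants will complete four additional questionnaires at baseline, and 16-weeks follow-up": Rose, LASA, PHQ-9 and PSS. Neither the Schedule of events nor Statistical Analysis contains an arm guess or any other check on blinding.

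**The concern.** The masking hides how the device looks. It does not hide whether a current is felt, and felt current is how the active arm is dosed. A participant who helps the instructor set the current for each muscle group, and then has it raised during the session, has direct evidence that it is on. A participant with zero output has nothing to report and nothing to adjust.

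The control arm does similar exercise so that a difference between groups can be credited to the current. For outcomes that a participant rates or works hard for, knowing the arm offers a second explanation: expectation. The Hypotheses section predicts significant improvement in these outcomes, and a report describing the trial as participant-blinded would have no data to show whether that was so.

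**Working it through.** The plan gives no figure to reproduce. The check sets the blinding statement beside the session rules, all within Intervention unless stated.

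| Feature | Intervention group | Control group |
|---|---|---|
| Vest, dress, display | Active device | Same appearance |
| Exercise | Low-amplitude, no added weights | Similar programme |
| Current | High intensity | None, or an undefined subthreshold level |
| Effort target for setting current | 6–7 of 10 | Not stated |
| Action at each 3-minute point | Current raised slightly | Not stated |

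**Step 1: could the effort rule cover both arms?** If it did, the instructor would have to raise a control participant's current toward a target of 6–7, and the sham would end. If it does not, the sessions differ in something the participant can feel. Either way a sentence is missing.

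**Step 2: how often does the contrast occur?** Inputs: a raise every 3 minutes; sessions of 14 minutes lengthening to at most 20 after 4 weeks; 16 weekly sessions.

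- 14 minutes: raises at 3, 6, 9 and 12 = 4.
- 20 minutes: raises at 3, 6, 9, 12, 15 and 18 = 6.
- Four short and twelve full sessions: 4 × 4 + 12 × 6 = 88.
- Range: 16 × 4 = 64 to 16 × 6 = 96. If raises begin only after week 4: 12 × 6 = 72.

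Controls have none written. This counts opportunities to notice the arm; it does not measure bias.

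**Step 3: which outcomes are exposed?** Outcomes and Measurements says of EndoPAT that "it allows continuous recording of the signal, and interpretation of the data is operator independent", and also that the method makes the signal independent of what the participant knows or consciously controls. The single primary aim is therefore largely protected. Mainly exposed are VO2 max (secondary aim iii), chest and leg press strength and power (iv), and LASA, PHQ-9 and PSS (vi): three of the eight secondary aims.

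**Step 4: what could expectation do?** The documents give no effect size, so this is illustration only. Assumptions: 40 per arm (80 randomised 1:1, no dropout), a two-sample t-test at two-sided 0.05, no true EMS effect, and an expectation effect of d SD. The noncentrality is d × √(40/2) and the critical value is 1.991 on 78 df.

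| Assumed d | Noncentrality | Chance of a significant result favouring EMS |
|---|---|---|
| 0 | 0 | 2.5% |
| 0.1 | 0.447 | 6.4% |
| 0.2 | 0.894 | 14.1% |
| 0.4 | 1.789 | 42.3% |

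The point does not depend on this table.

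**The case against.** The strongest reply is that the control arm is already a considered sham: similar exercise, same equipment, a device that appears to work. That is correct, and a reader might wrongly infer that controls have no matching routine at all. Only the intensity adjustment is unmatched.

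Second, the word subthreshold might mean a current that is felt but does not contract the muscle. That would soften the conflict, but the plan does not say so and names zero current as an alternative.

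Third, the sentence on 3-minute raises refers to a supplemental video that was not available, nor were the figures or consent pages. Details there could close part of the gap, so the statements about what is absent apply only to the text seen.

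Fourth, a reader might count the Rose questionnaire and the sensorimotor tests as equally exposed, making five of the eight aims. The documents do not support equal weight. Rose measures angina in a cohort that excludes cardiovascular and coronary disease, so it probably has little room to improve. Balance is computed from force-plate data and posture from static pictures.

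Fifth, opposite-arm pairs might be inferred from the trainer ratio. Because the ratio is stated separately for each arm, same-arm pairs may be intended. The share of mixed pairs could be anything from 0% to 100%, so it adds nothing to the size of the problem.

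Finally, an arm guess has limits. A guess late in the trial mixes unblinding with perceived benefit, and asking at week 8 could prompt speculation before the week 16 questionnaires. This stands, and it shapes the fix.

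**Conclusion.** The concern holds in a limited form. On the available text, participant blinding is unlikely to survive the session rules, certainly under the zero-current option, and the plan has no way to show otherwise. The contrast recurs 4 to 6 times per session, or 64 to 96 times per active participant over 16 sessions.

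Two stronger readings should be resisted. One is that every participant would know their arm: the text makes unblinding likely but does not prove it, and a felt, non-contracting control current could reduce it. The other is that the primary result is compromised: the plan describes RH-PAT as operator independent and independent of the participant's knowledge. It is called largely rather than fully protected because participants who know their arm could still change their habits or drop out.

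The amount of bias in LASA, PHQ-9, PSS, VO2 max and strength and power is unknown. The 6% to 42% range in the working follows entirely from assumed expectation effects of 0.1 to 0.4 SD and should not be quoted as an estimate.

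**What to change.** In Intervention:

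1. State which control current is used: zero, unfelt, or felt without contraction.
2. State that the effort rule raises current in the intervention group only. In controls, the instructor asks the same effort question and handles the device at the same 3-minute points, with output unchanged.
3. Train only same-arm participants together.
4. If the control current is zero or unfelt, replace the statement that "study participants will be blinded to whether or not they are receiving percutaneous electrical stimulation" with one saying that participants will not be told their allocation. Say in Statistical Analysis that self-reported and effort-dependent secondary results will be interpreted accordingly.
5. If participant blinding is still claimed, ask each participant once to guess their arm, at week 16 after the questionnaires and effort tests. Report correct guesses by arm descriptively, and exclude nobody on this basis. With 40 in an arm and 50% correct, the 95% interval is ±1.96 × √(0.25/40) = ±15.5 percentage points, enough to describe but not to serve as a decision rule.

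The cost is a few sentences, an instructor routine and at most one question at an existing visit. Same-arm pairing restricts scheduling, since partners must be free together each week; with 40 per arm it means 20 pairs in each. Under item 4 the trial gives up part of its blinding claim. The choice of control current stays with the sponsor. If training has already begun under this version, the current in use should be stated rather than changed, and the date on which mock adjustments start should be recorded. Sample size, endpoints and planned tests are unaffected.

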| | | | | 
at aerobic threshold in all groups (exEMS: + 29.6 %, p < 0.001; limEMS + 17.5 %, p < 0.001)
 
EF increased from 36.94 ± 8.6 to 42.36 ± 9.1 % (+ 14.7 %, p = 0.003) in the extended EMS group and 37.7 ± 3.6 to 40.3 ± 5.9 % [+ 6.9 %, p = 0.18] in the limited EMS group
 | |
| Wittman et al. Clinical Interventions in Aging 2016 | To determine the combined | Community dwelling women ≥ 70 years with | Randomized controlled trial: 6 months of WB-EMS with | Metabolic syndrome Z-score decreased in both groups; | No safety concerns or adverse effects were described |

| | | | | | |
|---|---|--------------------------------------|--|--|--|
| 
Impact of whole body electromyostimulation on cardiometabolic risk factors in older women with sarcopenic obesity: the randomized controlled FORMOsA-sarcopenic obesity study (87)
 | 
effect of WB-EMS and protein supplements on the metabolic syndrome in elderly community dwelling women with sarcopenic obesity
 | 
sarcopenic obesity N = 75
 | 
or without protein supplementation (150 kcal/day, 56% protein) vs. a non-intervention control group (n=25 in each group) WB-EMS included one session of 20 minutes (85 Hz, 350 μs, 4 s of strain–4 s of rest) per week with moderate-to-high intensity
 | 
however, changes compared with the control group were significant ($P=0.001$) in the WB-EMS&P group only On analyzing the components of the metabolic syndrome, significant positive effects for both WB-EMS groups were identified for mean arterial pressure, while the WB-EMS group significantly differed for
 | |
|---|---|--------------------------------------|--|--|--|

| | | | | | |
|--|--|--|--|---|--|
| | | | | 
waist circumference, and the WB-EMS&P group significantly differed for HDL-cholesterol ($P=0.006$) from the control group
 
No significant differences were observed between the WB-EMS groups
 | |
|--|--|--|--|---|--|

Efficacy and Safety Considerations

In voluntary strength training, the resistance of additional weight regulates the training intensity due to the maximum voluntary contraction (MVC), which is defined as one repetition maximum. In contrary to voluntary exercise, EMS activates muscle contraction artificially without using a resistance load. For this reason, it is not possible to simply transfer conventional training

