An important issue that has arisen with EMS training is the potential risk of elevation in blood creatinine kinase levels. Studies investigating the effects of EMS on creatinine kinase levels have shown that the electrical stimulus from EMS can cause significantly more stress to the muscular system and therefore could lead to higher creatinine kinase levels compared to voluntary muscle contraction exercise (88, 91). Indeed, due to the ability to innervate large muscle areas simultaneously with dedicated individual intensity to each muscle group, EMS can be associated with potential muscle injury. One study showed that, compared to traditional strength training, the stress on the muscular system is about 40% higher after intensive EMS (88). The authors arrived at the conclusion that the level of stimulation intensity is responsible for the elevation in creatinine kinase, while the duration of stimulation had no influence. The authors also showed that subjects still exhibited high values after long periods ranging from 24 hours to 4 days. Further stimulation within this time of decomposition would result in a cumulative rise in creatinine kinase levels (88), which in turn could overstress the muscular system further. Further, one study in which whole body EMS was implemented to the point of exhaustion in healthy novices confirmed very high elevations in creatinine-kinase levels. Although this study did not detect any of the reported clinical consequences of this “severe” rhabdomyolysis, in less fit subjects who are neither optimally prepared nor supervised, initial whole body EMS to exertion may have more far-reaching consequences. Consequently, EMS requires a greater interval between training sessions to prevent overstressing the muscular system and to ensure strength adaptations compared to conventional training. Of note, a subsequent whole body EMS conditioning phase of 10 weeks completed by a second EMS test application to exhaustion demonstrated creatinine-kinase peaks in the range of conventional resistance exercise

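### The Intervention section sets one effort target (RPE 6–7) with no start week; this departs from the easier early sessions in the protocol's own safety guideline, and no text says which governs

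*Combined protocol and SAP*

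**What the plan says.** The Intervention section makes perceived effort the control on stimulation: "The intensity of the stimulation will be regulated using a rate of perceived exertion (RPE) scale". It gives one target: "participants will be encouraged to exercise at a RPE of “6–7 out of 10” (i.e., “hard+ to very hard" on the Borg CR10 scale.

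Two other things change over time. Session length rises, by "extending the length of the session from 14 up to 20 minutes after 4 weeks of training". Current is also adjusted: start settings are determined after weeks 4, 8 and 12, and "the impulse intensity will be increased slightly every 3 minutes to maintain/slightly increase the prescribed RPE during each session".

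The section headed Guidelines for safe and effective WB-EMS, repeated in Figure 4, describes the early period differently. Training item 3 advises a shortened first session felt as 'a bit hard'. Training item 2 says that the highest level, labelled 'hard' to 'hard+', comes only after 8–10 weeks of training at the earliest. Separately, Efficacy and Safety Considerations says that a short conditioning period should be mandatory, without giving its length or effort level. That section cites Figure 4 only as a source of further safety considerations.

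**The concern.** Trainers have to carry out this instruction, and for the early sessions the protocol gives them two different answers. A trainer who applied the Intervention section as written in session one would depart from the guideline printed in the same document.

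Effort is the relevant control. Efficacy and Safety Considerations reports a conclusion that "the level of stimulation intensity is responsible for the elevation in creatinine kinase, while the duration of stimulation had no influence". On that account, shorter early sessions do not replace a lower early intensity.

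Entry requires no EMS experience, and people doing more than 45 minutes a week of other resistance training are excluded, so many participants may be beginners. Creatine kinase is scheduled at baseline, week 8 and week 16 only, so no scheduled test falls between baseline and week 8, when the instructions differ.

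There is also a cost to the estimate. If each trainer settles the early effort level alone, the dose behind any treatment difference is not reproducibly defined.

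**Working it through.** The plan states no figure on this point, so there is none to reproduce. The check is a comparison of texts and a count of sessions.

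**1. The two texts side by side**

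| Aspect | Intervention section | Guideline (Training items 2–4; Figure 4) |
|---|---|---|
| Effort in the first session | No separate value; the only target is RPE 6–7 | 'A bit hard' (advised) |
| Earliest time for highest effort | Not stated | After 8–10 weeks |
| Highest effort label | 'Very hard' | 'Hard+' |
| Early session length | 14 minutes, rising to 20 after 4 weeks | 5 minutes' familiarisation plus 12 minutes' load at first (advised), never above 20 |
| Frequency | Once weekly | At most once weekly for the first 8–10 weeks |
| Which text governs | Not stated | Not stated |

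The texts agree on frequency and are close on length. They differ on effort.

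**2. Do the other adjustments supply an effort ramp?** Lengthening the session changes duration. The rises in current serve to hold or slightly increase the prescribed RPE, so they presuppose the target. Asking for an intensity that is sufficient but tolerable sets no early ceiling. None of these lowers the effort target at the start.

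**3. Level as well as timing.** By the documents' own labels, the Intervention range begins at 'hard+', the top of the guideline's peak range, and extends to 'very hard'. The upper end therefore exceeds the guideline even after week 10. The guideline gives words and no numeric scale, so this comparison rests on labels alone.

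**4. Sessions in the period of difference**

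- EMS arm: 80 randomised 1:1, so 80 / 2 = 40.
- By the text (once weekly for 16 weeks): 8/16 = 50% to 10/16 = 62.5%.
- By the schedule row "Exercise with EMS device | X | X | X | X | X", whose columns are day 0, weeks 1–7, week 8, weeks 9–15 and week 16: 1 + 7 + 1 + 7 + 1 = 17 sessions.
- Before week 8: 1 + 7 = 8. Before week 10: 1 + 7 + 1 + 1 = 10.
- Shares: 8/17 = 47.1% to 10/17 = 58.8%.
- Participant-sessions at full attendance: 40 × 8 = 320 to 40 × 10 = 400, out of 40 × 17 = 680 by the schedule or 40 × 16 = 640 by the text.

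These are sessions for which the two texts give different effort instructions. How many would be run at RPE 6–7 cannot be derived, because no start week is given.

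**The case against.** The Intervention section never says that RPE 6–7 applies from session one. It speaks of encouragement, tolerability and close interaction with the instructor. It also presents itself as a brief account of an existing regimen: "we plan to implement the same previously utilized whole body-EMS training protocol successfully applied in other whole body-EMS trials". The cited reports and the supplemental video are not available here and may contain a lower early effort. This stands, and it means that a ramp may exist in practice. It does not tell a trainer who reads this protocol what to aim for in week 1.

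The safeguards are real. Once-weekly training meets the guideline's limits on frequency and on spacing of at least 4 days. One trainer handles at most two people. Sessions are shorter in the first four weeks. Kidney disease and rhabdomyolysis are exclusions. Among the earlier trials tabulated, two trained more often than this one (1.5 sessions a week; 3 sessions per 2 weeks) and reported no adverse effects. Another, with the same frequency, pulse settings and session length, trained once "per week with moderate-to-high intensity" and had no safety concerns described. None of these entries gives a start week for RPE 6–7, so they reassure without settling the point.

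Three stronger readings are tempting, and the documents do not support them.

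- A reader might infer that the whole guideline ramp is mandatory. In Training item 2, 'must' governs the successive rise in stimulation level or current. A fixed RPE can satisfy that, since current has to rise as people acclimatise. The 8–10 week limit is firmly worded, but the 'a bit hard' start is advice.
- A reader might infer that beginners will be harmed. The study of novices with very high creatine kinase used EMS to exhaustion, not supervised RPE 6–7.
- A reader might take the three-week acclimatisation time as the length of the conflict. It describes muscle adaptation and the creatine kinase response; it is not an effort instruction. The 14-minute sessions of the first four weeks can fairly be read as the conditioning period.

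**Conclusion.** The point holds as an unresolved inconsistency in a safety instruction and should be fixed. The Intervention section has one effort target, no start week and no lower early value. The guideline has a lower start and a later peak. Neither text is ranked above the other.

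About half or more of the sessions fall where the texts differ. The count assumes full attendance and takes the guideline's 8–10 weeks as the boundary. Early over-exposure is possible, but the documents do not show that it would occur. Confidence is medium, because the source regimen might close the gap.

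**What to change.** Amend the Intervention section so that:

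1. the first session targets 'a bit hard', with reduced duration;
2. the effort target then rises in steps at the existing week 4 and week 8 settings;
3. the week from which RPE 6–7 applies is stated;
4. the guideline governs early sessions wherever the two texts conflict.

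If 'very hard' stays as the upper end, give the reason for going above the guideline's highest level.

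Whether RPE 6–7 begins at weeks 8–10 or sooner is for the investigators to choose and justify. Starting then would leave 17 − 10 = 7 to 17 − 8 = 9 scheduled sessions at full target (6 to 8 on a count of 16). A later start lowers the dose, and Efficacy and Safety Considerations warns that too low a load can give no significant gain. It may also depart from the regimen that the trial sets out to replicate. An earlier start needs a justification against the guideline and the call for conditioning.

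The amendment itself costs wording and trainer instruction, with no added visits or participants. A gentler first session with stepwise rises takes a little off the early dose.
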